9.4.3 Sensitivity and Supplementary Analyses for Ranked Secondary Efficacy Endpoints

There will be no sensitivity analysis for ranked secondary efficacy endpoints.

9.5 Additional Efficacy Endpoints and Analyses

All additional efficacy endpoints are as defined in Section 3.3.

Analyses of additional efficacy endpoints will be conducted as specified in Section 9.1 by providing descriptive statistics and comparisons as needed.

9.6 Efficacy Subgroup Analyses

Subgroup analyses of the primary endpoints will be summarized descriptively based on following subgroups:

- Sex (male, female)
- Race (white, non-white)
- Age group (< 40, ≥ 40 to < 65, ≥ 65)
- Ethnicity (Hispanic or Latino vs. Not Hispanic or Latino)
- BMI (normal: < 25; overweight: ≥ 25 to < 30; obese: ≥ 30)
- BSA (< 10%, ≥ 10%)
- Prior biologic therapies for psoriasis (0, ≥ 1)
- Weight (≤ 100 kg, > 100 kg)
- Baseline sPGA (3, 4)
- Baseline sPGA-G (3, ≥ 4) for Study-G only
- Baseline scalp IGA (3, 4) for Study-S only
- Baseline PSSI (by median) for Study-S only

Age ≥ 65 years or BMI ≥ 30 subgroups will be combined with the adjacent subgroup when having fewer than 10% subjects.

The Breslow-Day test will be performed to assess the homogeneity of treatment effect across subgroups.

10.0 Safety Analyses

10.1 General Considerations

Safety data will be summarized for the Safety Populations. Safety summaries will be presented by the treatment group. Subjects are analyzed based on the treatment actually received, determined by the first dose of study drug received during the analysis period.

The overview of treatment-emergent adverse events (TEAEs) and Potentially Clinically Significant (PCS) findings in laboratory variables and vital sign variables will also be summarized among the Safety Populations.

10.2 Adverse Events

Adverse events (AEs) will be summarized and presented using primary MedDRA System Organ Classes (SOCs) and preferred terms (PTs) according to the version of the MedDRA coding dictionary used for the study at the time of database lock. The actual version of the MedDRA coding dictionary used will be noted in the AE tables and in the clinical study report. Specific adverse events will be counted once for each subject with multiple occurrences of the same AE for calculating number and percentages, unless stated otherwise. In addition, if the same adverse event occurs multiple times within a subject, the highest severity will be reported in severity summaries, and the worst/highest level of relationship to investigational product will be reported in the relationship summaries.

Unless specified otherwise, all the adverse event tables and listings will be provided for Period A (for subjects in Safety S and Safety G Populations) and Period B (for Safety B Populations). Adverse event tables will also be provided for ALL RZB Populations.

10.2.1 Treatment-Emergent Adverse Events

A treatment-emergent adverse events (TEAEs) in Period A for both Study-G and Study-S is defined as any AE worsened or newly occurred on or after the first dose of study drug in Period A and within the minimum of (140 days after the last dose of study drug in

Period A, one day before the first dose date in Period B if not missing [and the cutoff date during the Primary Analysis for Period A]).

A TEAE in Period B for both Study-G and Study-S is defined as any AE worsened or newly occurred on or after the first dose of study drug in Period B and within 140 days after the last dose of RZB in Period B.

A TEAE during the administration of RZB (i.e., among the ALL RZB G and ALL RZB S Population) is defined as any AE worsened or newly occurred on or after the first dose of RZB and within 140 days after the last dose of RZB [and the cutoff date during the Primary Analysis for Period A].

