11 START AND COMPLETION OF THE STUDY

The start-of-study is defined as the date of the first site activated.

The end-of-study is defined as the date of the last follow-up call (20 weeks after last dose), as indicated in [Appendix D](#) in the last country where the study is conducted.

The completion of the study for a subject is defined as one following:

- The date of the follow-up call (20 weeks after the last dose), as applicable
- The date of the Week 52 visit (for subjects who enter the optional CTE)
- The date of the last study visit (for subjects who prematurely discontinue and do not consent and/or complete to the follow-up call)
- The date of commercial risankizumab initiation (for subjects who initiate commercial risankizumab)

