12 OPTIONAL CONTINUOUS TREATMENT EXTENSION (CTE)

Purpose

To provide study completers with continuous treatment of risankizumab with the aim to ensure uninterrupted care in accordance with local regulations until commercially available and/or the subject has reasonable access to the treatment locally or transition to a separate CTPP OLE study.

Efficacy Variables

There are no defined efficacy endpoints for CTE.

Safety Endpoints

In the CTE, safety evaluation will include AE monitoring and concomitant medication updates. Additional procedures required for safety assessment will be conducted locally, per the investigator's discretion and local standard of care.

Overall Study Design and Plan

Eligible subjects may continue to receive open-label treatment with risankizumab in CTE to bridge the gap between completion of study and commercial availability and/or local treatment access to risankizumab or availability to enroll in a separate CTPP OLE study in the respective market. Continuing with CTE visits does not preclude a subject from being considered as completing the trial (Completion Visit at Week 52). CTE visits for the purposes of continued treatment are optional and occur following subject's completion of the trial.

[figure not shown]
In the CTE, subjects will be evaluated per standard of care and will return every 12 weeks (\pm 14 days) to continue administration of risankizumab (where locally permitted), as well as evaluation of AEs, SAEs, and use of concomitant medications. Efficacy data will not be collected.

Open-label risankizumab will be administered every 12 weeks starting at Week 52.

The 20-week follow-up phone call following the last dose of risankizumab in CTE will not be required for any subject who initiates commercial risankizumab or transitions to CTPP OLE study.

If risankizumab treatment is not available commercially via local access or through a CTPP OLE study, CTE will continue until all participating subjects have an option available for continued treatment or no longer derive benefit from receiving risankizumab and are discontinued.

Figure 2. CTE Schematic

Concomitant Medications

For subjects who receive open-label treatment with risankizumab in the CTE starting at Week 52, addition or modification of concomitant medications can be made per the investigator's judgment.

Withdrawal and Discontinuation of Subjects

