Subjects will be withdrawn from the CTE if any of the following occur in addition to what is stated in Section 5.5:

- A subject no longer derives benefit from risankizumab per investigator assessment.
- Subject has reasonable access to commercial risankizumab in the country of participation per investigator and/or sponsor assessment.
- Subject receives a live vaccine (with exception of non-replicating live vaccines).

Drug Assignment

Subjects will have the option to receive continued treatment with open-label risankizumab in CTE if they completed the study (Week 52) and continue to tolerate and derive benefit from risankizumab treatment, but do not have risankizumab commercially available and/or do not have reasonable access to risankizumab.

Safety Considerations

If any urine pregnancy test is positive, a serum pregnancy test will be performed locally. If the serum pregnancy test is positive, study drug must be permanently discontinued. If the serum pregnancy test is borderline, it should be repeated ≥ 3 days later. If the repeat serum pregnancy test is:

- Positive, the study drug must be permanently discontinued;
- Negative, the subject can continue in the study;
- Still borderline ≥ 3 days later, this will be considered documentation of continued lack of a positive result and the subject can continue in the study (unless prohibited locally) in the absence of clinical suspicion of pregnancy and other pathological causes of borderline results.

A pregnant or breastfeeding female will not be eligible for continuation or be allowed to continue study drug.

Independent Data Monitoring Committee, Cardiovascular Adjudication Committee, Anaphylaxis Adjudication Committee

Not applicable for CTE data.

Statistical Analysis for Safety

Safety analysis for the CTE may be conducted separately as needed.

Refer to [Appendix E](#) for additional information.

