10.2.4 Treatment-Emergent Adverse Events per Patient-Years of Exposure

Exposure-adjusted TEAEs per 100 patient-years will be provided, where TEAEs per 100 patient-years of exposure are defined as the number of TEAEs divided by the total exposure in 100 patient-years.

Note that one event per preferred term per day per subject will be counted in the calculation of the number of TEAEs (i.e., a preferred term will not be counted twice on the same day for the same subject). The exposure-adjusted TEAE rate per 100 patient-years is calculated as:

$$100 \times \frac{\text{Number of TEAEs}}{\text{Total Patient Years}}$$

where total patient years in each period are defined below.

Total Patient Years in Period A:

Sum of study drug exposure in Period A, defined as:

- For subjects who do not continue into Period B:
 - minimum of (the last dose date in Period A + 140, the end of study date (if not missing) + 1 day, [and the Primary Analysis cutoff date for Period A + 1 day]) minus the first dose date in Period A
- For subjects who continue into Period B:
 - minimum of (the last dose date in Period A + 140, first dose date in Period B, the end of study date (if not missing) + 1, [and the Primary Analysis cutoff date for Period A + 1 day]) minus the first dose date in Period A

normalized by 365.25 and rounded to one decimal place.

Total Patient Years in Period B:

Sum of study drug exposure in Period B, defined as: the minimum of (the last dose date in Period B + 140 days, and the end of study date + 1 day) minus the first dose date in Period B, normalized by 365.25 and rounded to one decimal place.

Total Patient Years in the All-Risankizumab Treated Period:

Sum of study drug of RZB exposure, defined as the minimum of (the last RZB dose date + 140 days, and the end of study date + 1 day) minus the first RZB dose date, normalized by 365.25 and rounded to one decimal place.

10.2.5 Deaths, Serious Adverse Events, and Adverse Events Leading to Study Treatment Discontinuation

Treatment-emergent serious adverse events (SAEs), TEAEs leading to premature discontinuation of study treatment, and TEAEs leading to death will be summarized by SOC and PT and in listing format.

A listing of pre-treatment SAEs with onset dates prior to the first dose of study drug (or prior to randomization date if not dosed), and a listing of all deaths will be provided for all subjects.

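### For subjects who enter the treatment extension, the Period B adverse event window can run 56 days beyond the point where Period B patient-years stop

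*SAP*

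**What the plan says.** **Event window (numerator).** SAP 10.2.1 counts a Period B event from the first Period B dose and "within 140 days after the last dose of RZB in Period B". It gives no other limit. The Period A window in the same section does have one: it also stops "one day before the first dose date in Period B if not missing". The ALL RZB window runs for 140 days after the last RZB dose, without tying that dose to Period A or B.

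**Patient-years (denominator).** SAP 10.2.4 ends Period B exposure at "the minimum of (the last dose date in Period B + 140 days, and the end of study date + 1 day". The ALL RZB exposure has the same two limits. SAP 7.2 puts the same end of study cap on Period B concomitant medications.

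**Completion.** The SAP does not define the end of study date. Protocol 11 lists completion dates per subject. For most completers it is the 20-week follow-up call. Two groups can finish earlier: "The date of the Week 52 visit (for subjects who enter the optional CTE") and "The date of commercial risankizumab initiation (for subjects who initiate commercial risankizumab"). The same section also has a trial-level definition: "The end-of-study is defined as the date of the last follow-up call (20 weeks after last dose").

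**Extension.** Protocol 12 states: "Open-label risankizumab will be administered every 12 weeks starting at Week 52". Adverse events are recorded at CTE visits. On analysis it says: "Safety analysis for the CTE may be conducted separately as needed".

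**The concern.** A rate per 100 patient-years is interpretable only if events and exposure are counted over the same days. Here the exposure rule has an end of study cap and the event rule does not. For most subjects the cap makes no difference. For a CTE entrant it can, because completion falls at Week 52 while the 140 days after the Week 40 dose run on to about Week 60. The subject receives a further risankizumab dose at the start of that interval and continues to have adverse events recorded.

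Two things are at stake. Period B and ALL RZB rates, which are the trial's longer-term safety summary, could be too high for entrants. Events that arise after an extension dose could also be labelled as belonging to the 36-week open-label period. The Period A rule shows that the authors knew a window should close when the next dosing phase starts, so the missing cap looks like an omission.

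**Working it through.** **Inputs**
- Dosing and visit days (Activity Schedule, Protocol Appendix D): Week 16 = Day 113, Week 40 = Day 281, Week 52 = Day 365, follow-up call = Day 421.
- Event and exposure rules: SAP 10.2.1 and 10.2.4.
- Completion for CTE entrants: Week 52 visit (Protocol 11).
- CTE uptake: not given, so a range is assumed.
- Event rate: assumed constant over time. All three Period B doses are assumed given.

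**1. Reproduce the plan's own figure.** Week 40 = 40 × 7 + 1 = Day 281, and 281 + 140 = Day 421. This matches the scheduled day of the follow-up call.

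**2. CTE entrant, subject-level end of study date**
- Event window: Days 113 to 421 inclusive = 421 − 113 + 1 = 309 days.
- Exposure: min(421, 365 + 1) − 113 = 366 − 113 = 253 days.
- Days with events but no exposure: Days 366 to 421 = 56 days.
- Ratio: 309 / 253 = 1.22, so +22%.
- With ±7 days on the Week 40 and Week 52 visits, the gap is 42 to 70 days and the ratio 1.16 to 1.28.

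**3. Completer followed to the Day 421 call**
- Exposure: min(421, 421 + 1) − 113 = 308 days.
- Ratio: 309 / 308 = 1.003, which is immaterial.

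**4. Overall Period B rate.** With a share f of subjects entering the CTE, the rate relative to no entrants is 308 / [(1 − f) × 308 + f × 253].

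| Assumed uptake | Relative rate |
|---|---|
| 5% | 1.009 |
| 10% | 1.018 |
| 25% | 1.047 |
| 50% | 1.098 |
| 100% | 1.217 |

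**5. Alternative reading.** If the end of study date is the trial-level date, an entrant's exposure is 421 − 113 = 308 days and the rate mismatch disappears. Events on 56 days after a CTE dose would still be labelled Period B.

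**6. ALL RZB.** If Week 40 is taken as the last RZB dose, the window again ends at Day 421 and the same Days 366-421 are uncovered. If CTE doses count as RZB doses, the window lengthens with each one. A single CTE dose on Day 365 already carries it to 365 + 140 = Day 505, while exposure still stops at the Week 52 completion date + 1 day.

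**7. Commercial starters.** Under Protocol 11 their exposure ends one day after commercial risankizumab starts, but their event window is not shortened. The gap is of the same kind and its length depends on the start date.

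**8. After the fix.** Ending an entrant's window on the Week 52 completion date gives 365 − 113 + 1 = 253 event days over 253 exposure days, ratio 1.000. Ending it one day before the CTE dose, as in the Period A rule, would give 252 / 253 = 0.996.

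**The case against.** The strongest reply is that the numerator stops at Week 52 as well. Protocol 6.1 collects adverse events up to study completion, which for CTE entrants is the Week 52 visit. Protocol 12 places CTE visits after completion of the trial. The CTE has a separate consent and its own activity table, and adjudication does not apply to its data. Protocol 4.1 and SAP 2.2 even refer to the CTE as another protocol. On that view, later events are CTE data and would never reach a Period B table.

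This is a reasonable account of what was intended, but it does not settle what the SAP instructs. Operations Manual 4.1 collects all adverse events until 20 weeks after the last dose of study drug. Operations Manual 2.3 lists both adverse event assessment and study drug administration at CTE visits. No text excludes CTE events from the Period B or ALL RZB summaries, and the wording on a separate CTE analysis is permissive.

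Other parts of the reply stand:
- The mismatch depends on a subject-level reading of an undefined date.
- Uptake is probably low. The CTE is for subjects without commercial availability or reasonable access, while the sites are in the United States and five EU countries and the drug is approved for plaque psoriasis in the US and EU.
- For commercial starters the follow-up call is not required, so fewer late events are likely to be recorded.
- Percentages of subjects with events have no exposure denominator, so they are not inflated in this way, although they could include post-extension events.

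A reader might infer that patient-years stop at Week 52 for everyone, or that the reported rates will certainly be biased. The documents support neither. The early stop applies to CTE entrants, with a similar early stop for commercial starters, and the bias arises only if CTE-period events are in fact carried into the Period B tables.

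**Conclusion.** The concern holds in a limited form. The event rule in SAP 10.2.1 lacks the end of study cap that SAP 10.2.4 applies to exposure. Read literally, this can put 56 days of post-extension events into Period B with no patient-years: +22% per entrant, and about +1% to +5% overall at 5% to 25% uptake. The 50% and 100% rows in the table show how the effect scales and are not expectations.

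The result rests on a constant event rate, the scheduled visit days, the Protocol 11 subject-level completion date as the end of study date, and CTE events being available to the Period B programs. The ALL RZB summary has the same opening, and a larger one if CTE doses count. Completers followed to about Day 421 show no material mismatch. The randomised Period A comparison is unaffected.

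It might also be inferred that the protocol requires CTE events to be analysed separately, which would close the gap. It only allows this. The practical problem is that two programmers following the SAP could produce different Period B and ALL RZB rates.

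**What to change.** 1. In SAP 10.2.1, end the Period B and ALL RZB windows at the earlier of the last RZB dose in Period A or B + 140 days and the subject's end of study date.
2. Define that date per subject in the SAP, following Protocol 11: the Week 52 visit for CTE entrants, the commercial start date for commercial starters, and the follow-up call or last visit as applicable for others. Use the same definition in 10.2.4.
3. State that CTE doses do not extend either window.
4. List post-completion CTE events separately. Because Protocol 12 makes a CTE safety analysis optional, events removed from Period B could otherwise be reported nowhere.

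The cost is a few lines of SAP text and one listing. A few events after Week 52 move out of the Period B and ALL RZB tables. Events on the Week 52 visit day itself stay in Period B, and that day has matching exposure.

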10.2.2 Adverse Event Overview

An overview of AEs will be presented consisting of the number and percentage of subjects experiencing at least one event for each of the following AE categories in each Safety Population:

- Any treatment-emergent AE
- Any treatment-emergent AE related to study treatment according to the investigator
- Any severe treatment-emergent AE
- Any serious treatment-emergent AE
- Any treatment-emergent AE leading to discontinuation of study treatment
- Any treatment-emergent AE leading to death
- Any treatment-emergent Area of Safety Interest, as defined in [Appendix B](#).
- All deaths will be summarized:
 - Deaths occurring \leq 140 days after last dose of study treatment
 - Deaths occurring $>$ 140 days after last dose of study treatment

10.2.3 Treatment-Emergent Adverse Events by SOC and/or PT

Treatment-emergent adverse events will be summarized by SOC and PT; by maximum relationship to study treatment as assessed by the investigator (e.g., reasonable possibility or no reasonable possibility) and SOC and PT and by maximum severity and SOC and PT and by subject number and SOC and PT. Specific adverse events will be counted once for each subject for calculating percentages, unless stated otherwise. In addition, if the same adverse event occurs multiple times within a subject, the highest severity and level of relationship to investigational product will be reported.

In addition, treatment-emergent adverse events will be summarized by PT and sorted by decreasing frequency for the RZB group in Period A for Safety G and Safety S Populations, for the RZB/RZB group in Period B for Safety B G and Safety B S Populations, and for RZB group in ALL RZB Populations.

10.2.4 Treatment-Emergent Adverse Events per Patient-Years of Exposure

Exposure-adjusted TEAEs per 100 patient-years will be provided, where TEAEs per 100 patient-years of exposure are defined as the number of TEAEs divided by the total exposure in 100 patient-years.

Note that one event per preferred term per day per subject will be counted in the calculation of the number of TEAEs (i.e., a preferred term will not be counted twice on the same day for the same subject). The exposure-adjusted TEAE rate per 100 patient-years is calculated as:

$$100 \times \frac{\text{Number of TEAEs}}{\text{Total Patient Years}}$$

where total patient years in each period are defined below.

Total Patient Years in Period A:

Sum of study drug exposure in Period A, defined as:

- For subjects who do not continue into Period B:
 - minimum of (the last dose date in Period A + 140, the end of study date (if not missing) + 1 day, [and the Primary Analysis cutoff date for Period A + 1 day]) minus the first dose date in Period A
- For subjects who continue into Period B:
 - minimum of (the last dose date in Period A + 140, first dose date in Period B, the end of study date (if not missing) + 1, [and the Primary Analysis cutoff date for Period A + 1 day]) minus the first dose date in Period A

normalized by 365.25 and rounded to one decimal place.

Total Patient Years in Period B:

Sum of study drug exposure in Period B, defined as: the minimum of (the last dose date in Period B + 140 days, and the end of study date + 1 day) minus the first dose date in Period B, normalized by 365.25 and rounded to one decimal place.

Total Patient Years in the All-Risankizumab Treated Period:

Sum of study drug of RZB exposure, defined as the minimum of (the last RZB dose date + 140 days, and the end of study date + 1 day) minus the first RZB dose date, normalized by 365.25 and rounded to one decimal place.

10.2.5 Deaths, Serious Adverse Events, and Adverse Events Leading to Study Treatment Discontinuation

Treatment-emergent serious adverse events (SAEs), TEAEs leading to premature discontinuation of study treatment, and TEAEs leading to death will be summarized by SOC and PT and in listing format.

A listing of pre-treatment SAEs with onset dates prior to the first dose of study drug (or prior to randomization date if not dosed), and a listing of all deaths will be provided for all subjects.

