7.5 Statistical Analyses for Safety

The safety analyses will be carried out using the Safety_G and Safety_S populations for Study-G and Study-S, respectively, and will be based on treatments the subjects actually received. Safety will be assessed by AEs, physical examination, laboratory assessments, and vital signs. Analysis details will be specified in the SAP.

TEAEs in each analysis period is defined as follows:

A TEAE in Period A for both Study-G and Study-S is defined as any AE with an onset date on or after the first dose of study drug in Period A and within the minimum of 140 days after the last dose of study drug in Period A and first dose of study drug in Period B.

A TEAE in Period B for both Study-G and Study-S is defined as any AE with an onset date on or after the first dose of study drug in Period B and within 140 days after the last dose of study drug in Period B.

A TEAE during the administration of risankizumab (i.e., among the ALL_RZB_G and ALL_RZB_S Population) is defined as any AE with an onset date on or after the first dose of risankizumab and within 140 days after the last dose of risankizumab.

The number and percentage of subjects experiencing TEAEs will be tabulated using the MedDRA SOC and preferred term, by severity, and by relationship to the study drug as assessed by the investigator. Summaries (including percentages and events per 100 patient-years) of SAEs, deaths, AEs leading to discontinuation and ASI will be provided as well. Pre-treatment SAEs will be summarized separately.

For laboratory tests and vital signs, mean change from baseline and percentage of subject with evaluations meeting predefined Potentially Clinically Significant criteria will be summarized. A listing of all subjects with any laboratory value that is above Grade 3 of CTCAE will be provided.

Additional details for the safety analysis will be provided in the SAP.

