4.0 Analysis Populations

The following population will be used for the analyses.

The **Intent-to-Treat (ITT) Populations** include:

- ITT G, includes all subjects randomized in Study-G.
- ITT S, includes all subjects randomized in Study-S.

- ITT B G, includes all subjects randomized in Study-G and enter Period B.
- ITT B S, include all subjects randomized in Study-S and enter Period B.

The ITT G/ITT B G and ITT S/ITT B S Populations will be used for all efficacy analyses in Study-G and Study-S respectively. Subjects will be included in the analysis according to the treatment group to which they were randomized (as randomized).

The **Safety Populations** include:

- Safety G includes all subjects randomized to Study-G and received at least 1 dose of study drug.
- Safety S includes all subjects randomized to Study-S and received at least 1 dose of study drug.
- Safety B G includes all subjects randomized to Study-G and received at least 1 dose of study drug in Period B.
- Safety B S includes all subjects randomized to Study-S and received at least 1 dose of study drug in Period B.

For the Safety G/Safety B G and Safety S/Safety B S Populations, subjects will be analyzed according to treatment actually received (as treated), regardless of the treatment randomized. The treatment actually received is determined by the first dose of study drug that the subject received during the specific analysis period.

The **All Risankizumab Treated Populations** include:

- ALL RZB G: all subjects who receive at least 1 dose of RZB as the study drug in Study-G.
- ALL RZB S: all subjects who receive at least 1 dose of RZB as the study drug in Study-S.

All RZB treated populations will be utilized for a comprehensive safety summary of RZB.

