6.0 Study Treatment Duration and Compliance

For the Safety Populations, duration of treatment will be summarized by descriptive statistics of mean, standard deviation, median, minimum and maximum for each study for each period for each treatment group, as well as ALL RZB Population for each study.

Duration of each treatment for each period is defined as following:

Study Treatment Duration in Period A for ITT Populations:

- For subjects who do not continue into Period B:
 - minimum of (the last dose date in Period A + 84, the end of study date (if not missing) + 1 day, [and the Primary Analysis cutoff date for Period A + 1 day]) minus the first dose date in Period A
- For subjects who continue into Period B:
 - minimum of (the last dose date in Period A + 84, first dose date in Period B, the end of study date (if not missing) + 1, [and the Primary Analysis cutoff date for Period A + 1 day]) minus the first dose date in Period A

Study Treatment Duration in Period B for ITT B Populations:

- For subjects who continue into Period B:
 - minimum of (the last dose date in Period B + 84 days, and the end of study date + 1, [and the Primary Analysis cutoff date for Period A + 1 day]) minus the first dose date in Period B

Study Treatment Duration under the Administration of RZB (Applicable for ALL RZB Populations Only):

- minimum of (the last date of RZB + 84 days, the end of study date + 1) minus the first dose date of RZB.

Treatment compliance will be summarized by treatment groups for each period for each study based on the Safety G and Safety S Populations, by visit and overall.

Compliance in Period A for Safety Populations:

- For Period A, the possible subcutaneous injections can happen at Baseline and Week 4.

The compliance for RZB and placebo will be summarized by the percentage of planned subcutaneous injections which are administered at each dosing visit and overall during Period A.

Compliance in Period B for Safety B Populations:

- For Period B, the possible subcutaneous injections can happen at Weeks 16, 28, and 40.

The compliance for subjects continued RZB and switched from placebo to RZB will be summarized by the percentage of planned subcutaneous injections which are administered at each dosing visit and overall during Period B.

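### At a Week 16 report, all-risankizumab adverse event rates would stop counting events at the cutoff but keep counting patient-years

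*SAP*

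**What the plan says.** **Events counted.** SAP 10.2.1 counts ALL RZB treatment-emergent events from the first risankizumab dose to "within 140 days after the last dose of RZB [and the cutoff date during the Primary Analysis for Period A". The bracketed part applies at the Week 16 analysis.

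**Patient-years, ALL RZB.** SAP 10.2.4 takes the "minimum of (the last RZB dose date + 140 days, and the end of study date + 1 day" and subtracts the first risankizumab dose date.

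**Patient-years, Period A.** The same section limits Period A exposure by "the end of study date (if not missing) + 1 day, [and the Primary Analysis cutoff date for Period A + 1 day". Both Period A formulas, for subjects who enter Period B and for those who do not, carry the cutoff and the proviso on a missing end date.

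**Treatment duration, ALL RZB.** SAP 6.0 uses the "minimum of (the last date of RZB + 84 days, the end of study date + 1) minus the first dose date of RZB", again with no cutoff and no proviso.

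**Where the rates are used.** SAP 10.2.4 says "Exposure-adjusted TEAEs per 100 patient-years will be provided" and gives no timing. SAP 10.2 adds "Adverse event tables will also be provided for ALL RZB Populations", and SAP 4.0 says "All RZB treated populations will be utilized for a comprehensive safety summary of RZB". Protocol 7.5 plans "Summaries (including percentages and events per 100 patient-years) of SAEs, deaths, AEs leading to discontinuation and ASI will be provided as well".

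**The concern.** A rate per patient-year needs its events and its time to cover the same window. Here the events stop at the cutoff and the time does not.

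Under SAP 9.1 the primary analysis takes place once all ongoing subjects have completed Week 16. Many subjects will then be in Period B with no end-of-study date. The ALL RZB formula can be read two ways for them:

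1. The missing date is left out of the minimum, as in Period A. The subject is credited up to 140 days after the last risankizumab dose, including days after the cutoff on which no event can be counted. The rate comes out too low.
2. The missing date is not left out. The formula has no value for that subject.

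The populations concerned are those the SAP designates for its overall safety summary of risankizumab. The error on reading 1 makes the drug look safer than the data show.

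**Working it through.** The SAP states no ALL RZB patient-year or rate figure, so there is nothing to reproduce. The check applies the formula as written to the planned schedule and compares it with the same formula plus the two Period A terms.

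**Inputs from the documents.** Protocol Appendix D puts dosing on Days 1, 29, 113, 197 and 281, which is 0, 28, 112, 196 and 280 days after baseline. Subjects randomized to placebo start risankizumab at 112. The follow-up call is on Day 421, which is 420 days after baseline. Each study has about 100 subjects, 50 per arm.

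**Assumptions (not in the documents).** Uniform accrual over 6, 12, 18 or 24 months of 30.4375 days, doses on schedule, no dropout. The cutoff is either the last subject's Week 16 visit (end of accrual + 112 days) or eight weeks later (+ 168 days).

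**Formulas, in days per subject.**
- As written, reading 1: min(last RZB dose + 140, end of study + 1 if reached) − first RZB dose.
- Observable: the same minimum, also capped at cutoff + 1.
- Proportion by which the rate is too low: 1 − observable / as written.

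**Single subjects.**
- Cutoff on the Week 16 dosing day, risankizumab arm: 112 + 140 − 0 = 252 days as written; 112 + 1 − 0 = 113 observable.
- Same cutoff, placebo-to-risankizumab: 112 + 140 − 112 = 140 days as written; 113 − 112 = 1 observable.
- Between the Week 16 and Week 40 doses, the excess falls from 139 days on a dosing day to 56 days just before the next dose. After the Week 40 dose it falls from 139 to 0 by the end of study.

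**Per study of 100 subjects, patient-years on reading 1.**

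| Cutoff | Accrual (months) | As written | Observable | Excess | Rate too low by |
|---|---|---|---|---|---|
| Last Week 16 visit | 6 | 67.9 | 40.6 | 27.3 | 40.2% |
| | 12 | 83.8 | 64.3 | 19.5 | 23.2% |
| | 18 | 89.1 | 76.1 | 13.0 | 14.6% |
| | 24 | 91.7 | 82.0 | 9.7 | 10.6% |
| Eight weeks later | 6 | 82.0 | 55.9 | 26.1 | 31.8% |
| | 12 | 90.8 | 76.0 | 14.8 | 16.3% |
| | 18 | 93.8 | 83.9 | 9.9 | 10.5% |
| | 24 | 95.3 | 87.9 | 7.4 | 7.8% |

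**Reading 2.** A subject is ongoing if fewer than 420 days from baseline at the cutoff. With 12-month accrual and the earlier cutoff that is (420 − 112) / 365.25 = 84%. Across the four accrual lengths, the subjects with no formula value number 100, 84, 56 and 42 at the earlier cutoff and 100, 69, 46 and 34 at the later one.

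**Sensitivity to dropout.** With an assumed 10% dropout spread evenly over 52 weeks (400 simulated enrolments per scenario), the reading 1 figures become 39.8, 23.0, 14.3 and 10.5%, and 31.1, 15.9, 10.3 and 7.7%. Each moves by less than one percentage point.

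**The case against.** The strongest reply is about timing. No section schedules ALL RZB rates at Week 16. The primary analysis is tied to cleaned Period A data, and Protocol 7.5 names neither Week 16 nor ALL RZB when it plans rates. The bracket in 10.2.1 could serve only tables of numbers and percentages. SAP 10.2.4 omits the cutoff from Period B patient-years as well, which would fit both being final-analysis outputs, when end-of-study dates exist and the formula works.

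That reading is possible but is stated nowhere. Section 10.2.4 promises rates without restricting them to the final analysis, and the 10.2.1 bracket shows that ALL RZB events are meant to be counted at the cutoff. The version 3.0 entry in SAP 14.0 lists changes to the ALL RZB event definition and to the Period B duration, but none to 10.2.4. That fits a numerator revised without its denominator, though it does not prove it.

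Several narrower points stand:
- Reading 2 is the less natural one, since Period A shows how the SAP treats a missing end date.
- If ongoing subjects were dropped from the patient-years but their events kept, the rate would be too high, not too low.
- An ongoing subject whose last risankizumab dose was more than 140 days before the cutoff receives no excess time.
- The size depends on assumed accrual.

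None of these brings the event window and the patient-years into line.

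**Conclusion.** The concern holds, on the condition that ALL RZB rates are reported at the primary analysis. The ALL RZB rule in 10.2.4 is then wrong as written: it credits time in which no event can count, or it gives no value for ongoing subjects.

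On the first reading, rates are too low in every scenario tested, by about 8% to 40%. That range rests on assumed accrual and cutoff dates and shows the plausible order of size, not an established figure.

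The consequence is limited. The rates are descriptive and enter no hypothesis test. Period A rates, percentages of subjects with events, and the final analysis are unaffected. The change should be made, but it does not threaten the trial's main conclusions.

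**What to change.** In SAP 10.2.4, replace the end-of-study term in the ALL RZB patient-years with the Period A wording, "the end of study date (if not missing) + 1 day, [and the Primary Analysis cutoff date for Period A + 1 day", keeping last RZB dose + 140 days as the other limit and subtracting the first RZB dose date. Make the same change to the ALL RZB duration in 6.0, keeping its 84 days.

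If Period B results are also reported at the primary analysis:
- add the bracketed cutoff to the Period B event definition in 10.2.1;
- add the cutoff and the missing-date proviso to Period B patient-years in 10.2.4;
- add the missing-date proviso to the Period B duration in 6.0, which already has the cutoff.

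If ALL RZB rates are meant only for the final analysis, one sentence in 10.2.4 saying so settles the matter for the rates.

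The cost is a few words taken from the SAP itself, with no change to design or data collection. The one visible effect is that any ALL RZB rates reported at Week 16 would be higher than under reading 1 of the present formula.
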